2.3 Tertiary Aims

1. Is there a relationship between amount of weight loss or amount of physical activity during lifestyle modification and ovulatory response and pregnancy?
2. Does physical activity alone lead to healthier pregnancies (i.e. better gestational weight gain, blood pressure change, glycohemoglobin levels)?
3. Is there a biphasic effect of either weight loss or physical activity on conception and pregnancy?
4. Does lifestyle modification affect the menstrual cycle of regularly ovulating women?
5. Is this treatment more cost effective than immediately proceeding with empiric infertility treatment? (compare with AMIGOS data)
6. Does weight loss or physical activity increase sexual function and amount of intercourse?
7. Can sperm microarray identify couples more or less likely to conceive?
8. Does perceived stress and self-reported quality of life by husband and wife influence success? [Assess by SF-12 and PHQ-9]
9. Is length of luteal phase predictive of pregnancy outcome?
10. Is there a relationship between length of infertility and conception?
11. Is there a difference in pregnancy rate in the first vs. second vs. third vs. fourth cycle?
12. Does weight loss or physical activity reduce the rate of metabolic syndrome?
13. Does the baseline vaginal or stool microbiome effect response to treatment and outcomes.
14. Does treatment effect the stool or vaginal microbiome?
15. Is the stool microbiome heritable to offspring?

16. Are there changes in stress as determined by salivary biomarker of stress according to treatments?

[figure not shown]
3 Background

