10.3.2 Secondary Outcome Measurements

We will assess secondary outcomes including live birth, time to pregnancy, pregnancy loss rate [including ectopics and Pregnancies of Unknown Location (PULs)], multiple pregnancy rate, pregnancy complication rate including development of gestational hypertension and diabetes, mode of delivery, birth weight, neonatal complication rate, predictive factors for response including DNA polymorphisms, salivary biomarkers of stress, quality of life, and cost effectiveness. Additionally we will be examining changes in the microbiome and association with outcomes.

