10.4 Sample Size and Accruals

10.4.1 Sample Size and Power Calculations

Estimates used for the power calculation are based on our experience from the OWL PCOS and AMIGOS trials as provided in the preliminary data section. The primary outcome for this trial is a good birth outcome defined as an infant (singleton or twin) born at ≥ 37 weeks between 2500 and 4000g without a major congenital anomaly. We will examine the cumulative rates between groups. We anticipate the proportion of good birth outcomes to be 0.25 in the standard lifestyle intervention (physical activity and weight maintenance) arm and 0.40 in the Intensive lifestyle modification arm. We anticipate that there will be an increased proportion of good birth outcomes in each group beyond our preliminary data, as we will not actively prevent pregnancy during the lifestyle intervention; therefore, they will have an additional 16 weeks to conceive prior to initiating empiric treatment. A sample size of 190 per treatment arm will provide 80% power to detect a 0.15 absolute difference in the proportion of good perinatal births (0.25 in the standard lifestyle modification and 0.40 in the intensive group using a two-sided test having a significance level of 0.05. Although the randomization is stratified by two factors (recruitment site and BMI status), this factor was not taken into consideration for the power analysis to be conservative because accounting for the correlation of these covariates with the outcome would simply increase the precision, and hence, increase the power. The sample size has been inflated to a total of 380 participants to allow for a dropout rate of 20%. We believe this 20% dropout rate is a reasonable estimate based on current experience in our PPCOS I, PPCOS II, OWL PCOS, and AMIGOS trials. The table below summarizes other possible sample size scenarios having a 0.15 absolute difference in the proportion of good birth outcomes between the two treatment arms, all of which we would have excellent power to detect (**Table 11**).

Table 11: Sample size scenarios based on varying assumptions

Standard Lifestyle Modification: Physical Activity Arm having a Good Birth Outcome	Intensive Lifestyle Modification Weight Loss and Physical Activity Arm: Proportion having a Good Birth Outcome		Significance Level (alpha)	Power (%)	N per Arm (0% Dropout)	N per Arm (20% Dropout)
0.15	0.30		0.05	80	121	152
			0.05	90	161	202
0.20	0.35		0.05	80	138	173
			0.05	90	185	232

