10.9 Data Analysis

Primary analyses will use an intent-to-treat paradigm, wherein all randomized subjects are included according to their randomized treatment assignment, regardless of actual treatment received, protocol violations, etc. for the primary outcome. The data will be summarized using descriptive statistics for continuous variables (mean, standard deviation, number of observations, and percentiles) and frequency statistics (frequencies and percentages) for categorical variables. All hypothesis tests will be two-sided and all analyses will be performed using SAS software, (SAS Institute, Inc., Cary, NC) or R (open source).

Primary efficacy analysis will be done using a logistic regression model to compare the two treatment arms with respect to the primary outcome of a good birth outcome while adjusting for recruitment site and baseline BMI. The proportion of good birth outcomes in each treatment

arm will be reported, as well as the odds ratio (OR) and corresponding 95% confidence interval (CI). We propose a number of secondary analyses and acknowledge that the power of our study may be low for some of these outcomes. However, even if not significant, examination of these secondary endpoints will guide future research in the area of infertility treatment. Logistic regression models will be fit to binary outcomes, such as pregnancy status (yes/no), to assess differences in the treatment arms while adjusting for recruitment site and baseline BMI. For rare binary events, e.g., multiple pregnancy births or other adverse events, Firth's penalized likelihood approach to logistic regression will be used to address the issue of having a small number of events.⁹⁰ Effect sizes from the logistic regression models will be quantified using the OR and 95% CI.

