Participant Drop-out and Other Missing Data: While every attempt will be made to collect complete data and prevent drop-out, missing data are inevitable. The sample size has been inflated by 20% in anticipation of some drop-out such as participant retention issues (based on experience in the PPCOS I, PPCOS II, OWL PCOS, and AMIGOS studies). The mechanism for missing data (missing completely at random, missing at random, or missing not at random) will be examined prior to beginning the analyses. We will compare the available characteristics of those with missing data to those with complete data and attempt to predict missingness with available data using multiple logistic regression and calculating the area under the receiver operating characteristic curve.⁹³ If necessary, imputation techniques may be used,⁹⁴ and shared parameter models or random pattern-mixture models considered if the preliminary analyses suggest that the data are missing not at random so that individuals with missing data can be included in the analyses.

Statistical versus Clinical Significance and Multiple Testing: As our analyses are based upon defined hypotheses, we have not included corrections for multiple testing. While the issue of p-value adjustment for multiple testing has long been a topic of discussion in observational

epidemiology and clinical trials, it generally is accepted that p-values should not be the sole criterion for assessing relationships. Conclusions will be based on the preponderance of scientific evidence related to each hypothesis, considering point estimates and confidence intervals, as well as statistical significance. Nonetheless, findings with marginal statistical significance will be interpreted cautiously, taking into consideration whether multiple testing could have contributed to a type I error.

11 Data Collection, Site Monitoring and Adverse Experience Reporting

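### The no-correction rule in 10.9 also covers DNA polymorphism and microbiome analyses that name no marker and no number of features, leaving their false-finding rate uncontrolled

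*Combined protocol and SAP*

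**What the plan says.** The multiplicity rule is in the last paragraph of 10.9 Data Analysis: "As our analyses are based upon defined hypotheses, we have not included corrections for multiple testing". It makes no exception. The same paragraph adds two qualifications. A p-value alone is not to decide, since "Conclusions will be based on the preponderance of scientific evidence related to each hypothesis", with effect estimates and their intervals taken into account. It also says that "findings with marginal statistical significance will be interpreted cautiously, taking into consideration whether multiple testing could have contributed to a type I error".

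The marker analyses appear in three places:

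- 10.3.2 lists "predictive factors for response including DNA polymorphisms" among the secondary outcomes and adds: "Additionally we will be examining changes in the microbiome and association with outcomes".
- 2.2 Secondary Aim includes both DNA polymorphisms and the stool and vaginal microbiome.
- 2.3 Tertiary Aims asks whether the baseline microbiome affects response and outcomes (aim 13), whether treatment affects the microbiome (aim 14), and "Can sperm microarray identify couples more or less likely to conceive" (aim 7).

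No section names a polymorphism, probe, taxon or summary index. None gives a number of features, a significance threshold for markers, a false discovery rate procedure or a validation step. A two-sided 0.05 level is stated for the primary comparison only (10.4.1: "using a two-sided test having a significance level of 0.05"). For everything else 10.9 fixes sidedness alone: "All hypothesis tests will be two-sided".

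**The concern.** Leaving p-values unadjusted because the hypotheses are defined in advance is a recognised position. It is reasonable for a single primary outcome and a short list of clinical outcomes named beforehand. It needs the hypotheses to be written down. For the polymorphism and microbiome work the documents name a technology and a general target, not a hypothesis about any particular marker. If many features are tested one by one, the rule as written lets each be judged as though it were the only test.

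What is at stake is the secondary and tertiary marker reporting. Markers could be published as predictors of response when the procedure that found them would often have produced some in pure noise. Aim 7 raises the further issue that identifying couples is a prediction claim, and no out-of-sample check is planned for it. The only area under the ROC curve in 10.9 is for predicting missingness.

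**Working it through.** **The plan's own figure.** The documents give no error rate or feature count for the marker analyses, so the only stated figure to reproduce is the sample size in 10.4.1 and Table 11. With rates 0.25 and 0.40 (mean 0.325), two-sided alpha 0.05, 80% power, pooled variance and no continuity correction:

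n = [1.960 × √(2 × 0.325 × 0.675) + 0.842 × √(0.25 × 0.75 + 0.40 × 0.60)]² / 0.15² ≈ 152 per arm; 152 / 0.80 = 190.

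Both match Table 11, as do its other rows. The single primary test stays at 0.05, so nothing below bears on it.

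**Inputs for the marker question.**

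- Per-test level 0.05, two-sided: assumed, since the plan states 0.05 only for the primary test.
- Number of features m: not in the documents, so a range is shown.
- No true association for any feature.
- Independence first, then equal pairwise correlation ρ.

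**Independent features.** P(at least one false finding) = 1 − 0.95^m; expected number of false findings = 0.05 × m.

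| m | P(at least one) | Expected number |
|---|---|---|
| 5 | 0.23 | 0.25 |
| 10 | 0.40 | 0.5 |
| 20 | 0.64 | 1 |
| 50 | 0.92 | 2.5 |
| 100 | 0.994 | 5 |
| 200 | >0.9999 | 10 |
| 1,000 | about 1 | 50 |

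**Correlated features.** With equicorrelated normal test statistics and c = 1.96,

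P = 1 − ∫ [Φ((c − √ρ·x)/√(1−ρ)) − Φ((−c − √ρ·x)/√(1−ρ))]^m φ(x) dx.

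| m | ρ = 0.3 | ρ = 0.5 | ρ = 0.8 |
|---|---|---|---|
| 20 | 0.54 | 0.42 | 0.22 |
| 100 | 0.94 | 0.78 | 0.36 |
| 1,000 | about 1 | 0.9995 | 0.57 |
| 10,000 | about 1 | about 1 | 0.79 |

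Correlation lowers the chance of any false finding but not the expected number, which stays at 0.05 × m. At ρ = 0.8 and m = 100, a screen with at least one false finding has on average 5 / 0.36 ≈ 14 of them.

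**Does the caution about marginal findings catch them?** The median of the smallest p-value among m independent null tests is 1 − 0.5^(1/m): about 0.007 at m = 100 and 0.0007 at m = 1,000. Neither would ordinarily be called marginal.

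**After a correction.** Bonferroni at 0.05/m brings the chance of any false finding to about 0.049 at every m from 2 upwards under independence. Benjamini-Hochberg at q = 0.05 also holds it at or below 0.05 when no association is real and the tests are independent, and is no stricter than Bonferroni. For the cost, take a marker that splits the sample into two groups of 152 with rates 0.25 and 0.40. Power is 0.80 for a single test, 0.24 under Bonferroni at m = 100 and 0.10 at m = 1,000. These are lower limits for Benjamini-Hochberg.

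**The case against.** The strongest reply is that the documents never describe a large screen. The DNA is collected for pharmacogenomic studies (7.2, randomization visit), which could mean a short candidate list, and the microbiome questions could be met by a few summary measures. Section 10.9 does not let significance decide alone, and it presents the secondary analyses as possibly underpowered and as a guide to later research. Section 13.2 also provides for a Concept Protocol for minor studies and committee approval for ancillary ones, where error control could be set.

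Much of this stands as a limit on the claim. A reader might infer that false predictors are certain to be found. The documents do not support that, because it requires hundreds of roughly independent tests and no count is given. A reader might also infer that all three platforms are aimed at conception. Only aim 7 is; the DNA and microbiome texts speak of response, outcomes or treatment effect. Nor is the sperm microarray plainly inside the planned analysis. It does not appear in section 10, and 7.2 has semen stored for microarray work at a later date, subject to repository consent. That it inherits the rule is an inference, since 10.9 is the only multiplicity rule written.

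The reply does not rescue the rule. Even 5 to 20 independent markers give 23% to 64%. Weighing estimates and intervals does not help for markers chosen because they were extreme, since the same selection inflates those estimates. Section 13.2 makes later error control possible but does not require it. If a short list is intended, naming it would make the stated reason true.

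**Conclusion.** The concern holds in conditional form. The reason given for not correcting does not apply to the DNA polymorphism and microbiome analyses, and nothing in the plan controls their false-finding rate. How large the problem is depends on a feature count and a correlation structure that the documents leave open. Across the assumed range the chance of at least one false finding runs from about 22% (20 features, ρ = 0.8) or 23% (5 independent features) to practically 100% (200 or more independent features). All of these are several times 5%.

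The figures assume 0.05 per test and no real association. The primary analysis, the sample size and the named clinical secondary outcomes are outside this point. The text should be changed before any marker data are analysed, because a correction chosen afterwards could be guided by the results.

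**What to change.** In 10.9:

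1. Limit the no-correction sentence to the primary outcome and the named clinical secondary outcomes.
2. For DNA polymorphism and microbiome features, and for the sperm microarray when it is analysed, state the number of features tested on each platform. Control the false discovery rate within each platform and outcome, for example by Benjamini-Hochberg at q = 0.05.
3. Label markers that do not pass as hypothesis-generating.
4. If a predictive score is built for aim 7, report cross-validated performance with feature selection repeated inside each fold.

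This takes SAP wording and routine code, with no new participants or samples. The downside is lower power for single weak markers and fewer of them declared.

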11.1 Records to be kept

Data will be collected prospectively by designated research personnel at each study site, supervised by the site PI. Subject data will be entered into a web-based data management system created by the Data Coordination Center, using only a study ID number. Original source documents will be kept in the study subject folder.

11.1.1 Maintenance/Retention of site records

In order to comply with Good Clinical Practice (GCP) requirements, the investigators must maintain the master patient log that identifies all patients entered into the study for a period of two years after the study ends so that the subjects can be identified by audit. The PI must maintain adequate records pertaining to subjects' files and other source data for a minimum of 5 years after completion of the study.

11.2 Role of Data Management

Each clinical site and the DCC will be responsible for ensuring study personnel are trained and follow the data management guidelines of Good Clinical Practice and RMN policies.

11.3 Quality Assurance

The DCC will perform regular clinical site monitoring to assure protocol compliance, ethical standards, regulatory compliance and data quality at the clinical sites, including review of records available for inspection by monitoring authorities. These data will be shared with the Steering committee and the DSMB as needed. Regular face to face meetings, monthly conference calls, and phone conferences of the protocol committees and recruitment committees will be forums for addressing quality assurance issues.

11.3.1 Data Entry and Forms

Case Report Forms (CRFs) will be developed as the protocol is developed. They will also be implemented in a Web-based Oracle data management system. The Web data entry forms will be similar to the paper forms with the same questions. However, the Web forms usually have more flexibility than the paper forms, such as pull-down menus.

11.3.2 Features of Data Management System

Features of the data management system include study definition; different types of data entry (and complete audit trail); forms control; query capture, reporting, and resolution; dictionary coding of Adverse Events (AEs) and medical terms; and clinical data review Tools. The end-user/reporting/ad hoc query front-end uses a standard Web browser, so that data entry and browsing can be done from any machine with Internet access, without purchase of special software. Login to this system will be through a secured Web server with the security under the protection of Yale Center for Clinical Investigations.

11.3.3 Data Security

A data server and Web server will be used. The data server will be managed by YNHH IT center and the servers will be managed by Forte Research Systems. The web server will be accessible through a secured login, but the data server can only be accessed through the web server. For security purposes, no login to the data server will be permitted, and access to the back end is

limited to authorized individuals. PHI, including patient names and addresses, will be locked and secured at the participating sites, and data will be linked through a unique identification number, which will be assigned after a patient is screened or enrolled. Access will be limited to authorized individuals (21 CFR 11.10(d)). Each user of the system will have an individual account. The user will log into the account at the beginning of a data entry session, input information (include changes) on the electronic record, and log out at the completion of the data entry session. The system will be designed to limit the number of log-in attempts and record unauthorized access log-in attempts. Individuals will work only under their own access key, and not share these with others. The system will not allow an individual to log onto the system to provide another person access to the system. Users will be asked to change their passwords at established intervals commensurate with a documented risk assessment. This plan has been adapted from the guidelines for computerized systems used in clinical investigations established by the U.S Department of Health and Human Services Food and Drug Administration.

11.3.4 Data Quality Control

11.3.4.1 Competency to perform procedure/tests in the protocol

The site PI will be responsible for ensuring that study related tests are performed by competent personnel. The criteria for determination of competency may vary between sites in the study. Attempts will be made to standardize protocols whenever possible to minimize inter-site variation.

11.3.4.2 Quality Control Steps

Quality control of data will be handled on three different levels. The first level is the real-time logical and range checking built into the web-based data entry system. The research coordinators and data entry clerks at the participating sites are required to ensure the data accuracy as the first defense. The second is the remote data monitoring and validation that is the primary responsibility of the data manager and programmer at the DCC. The data manager will conduct monthly comprehensive data checks (SAS programs run on a regular basis as a systematic search for common errors and omissions), as well as regular manual checks (within the database system). Manual checks will identify more complicated and less common errors. The data manager will query sites until each irregularity is resolved. The third level of quality control will be the site visits, where data in our database will be compared against source documents. Identified errors will be resolved between our center and clinical sites. The visits will assure data quality and patient protection.

An audit trail will be added as another security measure. This will ensure that only authorized additions, deletions, or alterations of information in the electronic record have occurred and allows a means to reconstruct significant details about study conduct and source data collection necessary to verify the quality and integrity of data. Computer generated, time-stamped audit trails will be implemented for tracking changes to electronic source documentation.

Controls will be established to ensure that the system's date and time are correct. This is a multi-center clinical trial and will be located in different time zones. System documentation will explain time zone references as well as zone acronyms. Dates and times will include the year, month, day, hour, and minute to the date provided by international standard-setting agencies (e.g. US National Institute of Standards and Technology). The ability to change the date or time

will be limited to authorized personnel, and such personnel will be notified if a system date or time discrepancy is detected.

In addition to internal safeguards built into the computerized system, external safeguards will be implemented. Data will be stored at the Data Coordination Center. Records will be regularly backed up, and record logs maintained to prevent a catastrophic loss and ensure the quality and integrity of the data. This plan has been adapted from the guidelines for computerized systems used in clinical investigations established by the U.S Department of Health and Human Services Food and Drug Administration.

